that morning. After collecting vitals and testing a urine sample for pregnancy and to confirm abstinence from illicit drugs, participants will receive 50% of their prescribed methadone dose, which will be prepared by the BPRU pharmacy, to consume under staff observation at BPRU. This dose will produce modest suppression of participant opioid withdrawal for an acute period of time, which will provide an opportunity for them to become acquainted with the session procedures while still ensuring they will show prominent signs of withdrawal during the study period. Initial vitals and urine testing will take place at the BPRU. The participant then will be transferred to the CRU where they will remain until the end of the 3rd day. Participants will be assessed for symptoms of opioid withdrawal and complete measures of drug craving and anxiety periodically throughout Day 1. The first dose of study drug (placebo or Epidiolex) will be administered in the afternoon (e.g., 18:00 +/- 1:00 hour) on Day 1 at the CRU.

Participants will complete withdrawal ratings on a regular basis (e.g., every 4 hours) before and after study drug administration, except for when the participant is sleeping. This schedule will be based on the pharmacokinetic profile of CBD (21). Vital signs will also be measured every time withdrawal assessments occur (Figure 1).

[figure not shown]

Figure 1. Timeline of inpatient session with approximate timing for study procedures. Gray circles indicate when measures of opioid withdrawal. craving. and anxietv are assessed.

On Day 3, participants will complete a cue-induced craving task and a Cue-concurrent Choice Task, and a Methadone Valuation Task described below. Withdrawal ratings will continue up to study discharge on Day 3 and acceptability ratings of the study drug will be collected prior to discharge. Participants will be discharged in the afternoon on Day 3, one hour after finishing the Methadone Valuation Task. At any point a participant can elect to resume regular methadone dosing and remain at the unit to complete study participation. However, participants who take their dose before beginning the Methadone Valuation Task he or she will not be able to participate in the Methadone Valuation Task. Finally, before participants leave, medical staff will collect a blood sample to be tested for liver enzyme levels. For an overview of study procedures, please reference Figure 1.

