Epidiolex is an oral solution that will be purchased commercially, and our research pharmacy will prepare the dose and a flavor-matched control for placebo dosing. A recent pharmacokinetic study reported that a 750mg dose of Epidiolex, administered orally, reached peak concentrations in 5-6 hours after administration. The same study reported that a 1500mg dose of Epidiolex, administered orally, reached peak concentrations 6-7 hours after administration. CBD is highly lipophilic and subject to extensive first-pass metabolism via the CYP 1A1, 2D6, and 2C9 pathways, which yields an active metabolite (7-OH-CBD). 7-OH-CBD is believed to contribute to cannabidiol's efficacy for seizure control and has a half-life of 13.3 hours, with no evidence of psychoactive effects.

*b. Methadone Hydrochloride Oral Solution* will be administered to participants at their prescribed dose or less for its indicated use (maintenance therapy for opioid use disorder). Using our standard procedure, we will procure the participant's written permission to contact his or her provider to confirm (1) the participant's enrollment in a methadone maintenance program for opioid dependence, (2) the participant's daily dose of methadone and (3) the length of time the participant has been maintained on their current dose. Methadone will be administered in a way that is within the participant's normal dosing regimen with the exception that we will be administering it at our residential research unit and that one dose will be less than what is normally prescribed (Day 1), another dose will be omitted (Day 2) and the final dose may be delayed (Day 3). Methadone is a commercially-available Schedule II medication that is currently indicated for management of pain, detoxification treatment of opioid addiction and maintenance treatment of opioid addiction.

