#### N/A

#### 7. Study Statistics

a. Primary outcome variable.

Feasibility:

- Number of participants who complete the study as intended
- Peak change in withdrawal scores (Subjective Opiate Withdrawal Scale; SOWS) during abstinence-induced withdrawal- this will provides evidence that withdrawal will be sufficiently quantifiable to use this model to examine Epidiolex suppression of withdrawal in a large-scale R01-type trial.

Safety:

- Frequency of Adverse Events (excluding symptoms of opioid withdrawal) reported under each condition (0, 800mg CBD)
- Number of participants whose AST/ALT levels >3xULN at the end of the session according to a blood test at the end of the active drug condition

Initial Efficacy:

- Efficacy will be assessed by comparing the following outcomes between the active (CBD) and placebo-dosing sessions:
  - Withdrawal symptom suppression, measured through daily self-report ratings of withdrawal on the SOWS, evaluated as Total score and individual scores. Scores will be evaluated using area-under-the-curve for each day as well as peak daily rating.
  - Number of 30-minute intervals for which the participant selected money over methadone during the methadone evaluation task

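### Methadone may be resumed at any point with SOWS ratings continuing, but section 7 neither separates later ratings, nor reports resumption by condition, nor defines completion

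*Combined protocol and SAP*

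**What the plan says.** Section 4a, Session Procedures, gives a standing permission: "At any point a participant can elect to resume regular methadone dosing and remain at the unit to complete study participation". The one consequence it attaches concerns the Day 3 task: "participants who take their dose before beginning the Methadone Valuation Task he or she will not be able to participate". Rating does not stop at resumption: "Withdrawal ratings will continue up to study discharge on Day 3". The frequency is given as: "Participants will complete withdrawal ratings on a regular basis (e.g., every 4 hours) before and after study drug administration".

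Section 6a describes the intended methadone schedule in each session: a reduced dose on Day 1, none on Day 2, and a possibly delayed dose on Day 3.

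Section 7a lists SOWS, compared between the CBD and placebo sessions, under the primary outcomes (Initial Efficacy): "Scores will be evaluated using area-under-the-curve for each day as well as peak daily rating". Under Feasibility it lists "Number of participants who complete the study as intended" and the peak change in SOWS during abstinence.

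Nothing in section 7 says whether ratings after elective resumption are kept, dropped or analysed separately. Resumption is not an outcome in 7a or 7b. It is not a removal criterion in 4f or a discharge criterion in 7d. Section 7c says the results will be mainly descriptive and will serve as preliminary data for an R01 application.

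**The concern.** Methadone suppresses the symptom that SOWS measures; the protocol relies on this for the Day 1 half dose. A participant is most likely to ask for it when withdrawal is bad. If CBD works as hypothesised, resumption should be more frequent or earlier in placebo sessions. Those sessions would then contribute methadone-suppressed scores to the placebo side of the comparison, and the observed SOWS difference would be too small. Day 2, the one day with no scheduled methadone, is directly exposed, and so is Day 3 if suppression persists.

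The feasibility count has a related weakness. Section 2 makes feasibility of the withdrawal paradigm an objective. A person who resumes methadone on Day 2 and stays to discharge has completed participation in the sense of section 4a, although the withdrawal model was abandoned in that session. Without a definition, a favourable count could be carried into the R01 application. The choice to resume, itself informative about efficacy and feasibility, would go unreported.

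**Working it through.** **No plan figure to reproduce.** The documents give no sample size, effect size, SD or resumption rate. Every input below is an assumption in arbitrary SOWS units, chosen only to show direction and range. Differences are placebo minus CBD, so a positive value favours CBD.

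**Formula.** Let D be the true difference, L the amount by which resumption lowers the summary in a placebo session, and p the share of participants who resume on placebo only. With no resumption on CBD:

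observed difference = D − pL; zero at p = D/L.

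Resumption on CBD adds a term of the opposite sign.

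**Simple case.** Assume Day 2 mean SOWS of 30 on placebo and 24 on CBD, with resumption at mid-day bringing the remaining half of the ratings to 10. A resumed placebo session then averages (30 + 10)/2 = 20. So D = 6, L = 10, and the observed difference is 6 − 10p: 3 at p = 0.3 and 0 at p = 0.6.

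**Rising profile.** Assume unresumed placebo ratings on Day 2 at 08:00, 12:00, 16:00 and 20:00 of 14, 18, 22 and 26, and on Day 3 at 08:00 and 12:00 of 28 and 30 (no task dose taken by then). CBD lowers every rating by 20%. Resumption at 12:00 on Day 2 lowers all later ratings by 70%, lasting into Day 3.

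- Day 2 AUC, placebo: 4 × (16 + 20 + 24) = 240. CBD: 0.8 × 240 = 192. D = 48.0.
- Resumed placebo ratings: 14, 18, 6.6, 7.8. AUC = 4 × (16 + 12.3 + 7.2) = 142. L = 98.
- At p = 0.3: 48.0 − 0.3 × 98 = 18.6. Zero at 48/98 = 49%.
- Day 2 peak: D = 26 − 20.8 = 5.2. The resumed peak is 18, reached before resumption took effect, so L = 8. At p = 0.3: 5.2 − 2.4 = 2.8.
- Day 3 peak: D = 30 − 24 = 6.0; L = 30 − 9 = 21. At p = 0.3: 6.0 − 6.3 = −0.3.

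**Range.** The table shows the placebo-only share that brings the difference to zero, D/L, with the CBD effect at 10, 20 or 30% and suppression at 50 or 70%. A value above 100% cannot be reached.

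| Summary | Day 2 resumption | 10% effect, 70% suppression | 20%, 70% | 30%, 50% |
|---|---|---|---|---|
| Day 2 AUC | 08:00 | 16% | 32% | 68% |
| Day 2 AUC | 12:00 | 24% | 49% | over 100% |
| Day 2 AUC | 16:00 | 66% | over 100% | over 100% |
| Day 2 peak | 08:00 | 22% | 43% | 65% |
| Day 2 peak | 12:00 | 32.5% | 65% | 97.5% |
| Day 2 peak | 16:00 | 65% | over 100% | over 100% |
| Day 3 AUC or peak | any of these | 14% | 29% | 60% |

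The difference shrinks whenever placebo-only resumption lowers the ratings used. It reverses only beyond the shares shown.

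**Effect of truncation.** One remedy is to cut both sessions of a pair at the earlier resumption. On the same profile with a 20% effect, the full Day 2 mean difference is 0.2 × 20 = 4.0. Cut after the 12:00 rating it is 0.2 × 16 = 3.2. The peak difference falls from 5.2 to 0.2 × 18 = 3.6, and that pair's Day 3 ratings are lost. Truncation therefore can also shrink the difference, because it discards the later, more severe ratings.

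**The case against.** The best case against the point has several parts.

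- **Silence is not a rule.** A reader might infer that the plan requires ratings after resumption to enter the daily summaries. It does not say so; that is the natural reading of a plan that rates to discharge and summarises each day without exception.
- **Completion.** A reader might infer that someone who resumes is counted as a completer. The outcome is completing *as intended*, which is undefined and could be read to exclude such a session. The other feasibility measure is tied by its wording to abstinence and gives some protection.
- **Peak and Day 1.** If symptoms prompt the request, that day's peak may already have occurred. Little of Day 1 is at stake: a half dose of methadone is given that morning and study drug starts only at about 18:00.
- **CBD exposure on Day 2.** The protocol says four 12-hourly doses are needed for steady state. Counting from 18:00 on Day 1, the fourth falls at about 06:00 on Day 3, so Day 2 is not a full-exposure contrast.
- **Size.** The illustrations set resumption on CBD to zero and make suppression immediate, although section 6a puts peak methadone concentration at 1 to 7.5 hours. Taking methadone before the task also forfeits up to $100, which discourages it.
- **Purpose.** This is a descriptive pilot with safety and feasibility objectives and no efficacy decision rule.

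All of this limits the claim and its size. None of it supplies a rule for the affected ratings or a definition of completion. The descriptive purpose does not remove the problem, since a descriptive difference carries the same bias and is what the R01 application would show. Early resumption also leaves that session without a Methadone Valuation Task score, the other listed efficacy outcome.

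**Conclusion.** The point stands as a gap in section 7a that should be closed before the data are summarised. The comparison does not separate ratings made after elective resumption, and resumption itself goes unreported. If resumption is more frequent or earlier on placebo, the SOWS difference is biased toward zero; an excess on CBD biases it the other way. Daily AUC and later days' peaks are most exposed.

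A reader might infer that a CBD effect will be hidden or reversed. The documents do not support that: they give no resumption rate, and the result depends on a real CBD effect, on unequal resumption and on its timing. Under the assumed values, the placebo-only share that would cancel the difference runs from 14% to unreachable. On completion, the supported statement is only that the count may include sessions in which abstinence was abandoned.

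**What to change.** Change the wording of section 7a only, leaving untouched who may take methadone and when:

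1. Report the number and timing of elective resumptions by condition, as an efficacy and feasibility outcome beside SOWS.
2. Count a session as completed as intended only if no methadone was taken outside the scheduled Day 1 dose and the Day 3 task or end-of-task dose. Give this count by condition.
3. Present SOWS AUC and peak on all ratings, together with a sensitivity analysis that excludes ratings after elective resumption. One form is time-averaged SOWS over the matched clock window before the earlier resumption in the pair. State that this window loses later ratings and can itself shrink the difference, so neither analysis is free of bias.

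Section 4a speaks of regular dosing on elective resumption but sets all Day 3 doses at 50% of the prescribed dose. These passages should be reconciled so that scheduled and unscheduled doses can be told apart in the record.

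The cost is slightly more analysis work and a completion count that may look less favourable. Section 8b places all drug administration under staff supervision, so resumption times should be obtainable. The protocol does not say outright that they are recorded, and a line to that effect would help.

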# 5. Inclusion/Exclusion Criteria

Inclusion Criteria:

- Aged 18-55
- Medically cleared to take study medication
- Are not pregnant or breast feeding

- Willing to comply with the study protocol
- Provides urine that tests positive for methadone
- Maintained on 40-120 mg of daily methadone with no dose changes in the past 2 weeks (verified through a medical release with the participant's provider)

#### Exclusion Criteria:

- Meet DSM-5 criteria for past year alcohol/substance use disorder other than opioid use disorder
- Previous adverse reaction to a cannabinoid product
- Urine sample that tests positive for drug other than methadone
- Self-report any illicit drug use or cannabinoid use in the past 7 days
- Presence of any clinically significant medical/psychiatric illness judged by the investigators to put subject at elevated risk for experiencing an adverse events
- Past year suicidal behavior as assessed via the Columbia Suicide Severity Rating Scale
- History of seizure disorder
- Past 14 day use of any of the following contraindicated medications:
  - o Clobazam, Valporate
  - Moderate or strong inhibitors of CY3A4 or CYPC19 (with the exception of methadone)
  - Strong CYP3A4 or CYP2C19 inducers
  - UGT1A9, UGT2B7, CYP1A2, CYP2C8, CYP2C9, CYP2C19 substrates (with the exception of caffeine).
  - CNS depressants that are contraindicated with Epidiolex
- Breathalyzer that tests positive for alcohol prior to session admission
- Self-reported consumption of grapefruit juice within 24 hours of session admission
- Have a history of clinically significant cardiac arrhythmias or vasospastic disease
- Have circumstances that the study investigators believe are contraindicated with study participation and/or would interfere with study participation (e.g., impending jail).
- Moderate-severe hepatic impairment as indicated by ALT or AST levels > 3x ULN and/or Bilirubin levels >2x ULND as evidenced by a blood test.

#### 6. Drugs/ Substances/ Devices

a. The rationale for choosing the drug and dose or for choosing the device to be used.

Study Drugs: Cannabidiol and Methadone

a. *Cannabidiol (Epidiolex)* has been strategically chosen for this study because it is a widely-used, commercially-available Schedule V cannabinoid medication that is currently indicated for seizure control in persons with Lennox-Gastaut syndrome and severe infantile myoclonic epilepsy, but which could be prescribed off-label for the adjunctive treatment of clinical pain. **Epidiolex is the only FDA-approved formulation of cannabidiol and we are proposing to administer 800 mg**. Epidiolex has been administered safely to individuals with polydrug use in single doses up to 4500mg and in healthy participants in single doses up to 6000mg. In open-label clinical trials among individuals with epilepsy and tuberous sclerosis complex patients, Epidiolex was well tolerated at doses up to 50 mg/kg/day (3500 mg/day in a 70 kg person) for a 3-month period. Doses up to 1500mg twice daily were well tolerated among healthy adult participants for a 7-day period. Epidiolex is an oral solution that will be purchased commercially, the research pharmacy will prepare the dose and a flavor-matched control for placebo dosing. A recent pharmacokinetic study reported that a 200mg dose of Epidiolex, administered orally, reached peak concentrations in 2-3 hours and had a half-life of 8-9 hours. It is highly lipophilic and subject to extensive first-pass metabolism via the CYP 1A1, 2D6, and 2C9 pathways, which yields an active

metabolite (7-OH-CBD). 7-OH-CBD is believed to contribute to cannabidiol's efficacy for seizure control and has a half-life of 13.3 hours, with no evidence of psychoactive effects.

Epidiolex is an oral solution that will be purchased commercially, and our research pharmacy will prepare the dose and a flavor-matched control for placebo dosing. A recent pharmacokinetic study reported that a 750mg dose of Epidiolex, administered orally, reached peak concentrations in 5-6 hours after administration. The same study reported that a 1500mg dose of Epidiolex, administered orally, reached peak concentrations 6-7 hours after administration. CBD is highly lipophilic and subject to extensive first-pass metabolism via the CYP 1A1, 2D6, and 2C9 pathways, which yields an active metabolite (7-OH-CBD). 7-OH-CBD is believed to contribute to cannabidiol's efficacy for seizure control and has a half-life of 13.3 hours, with no evidence of psychoactive effects.

*b. Methadone Hydrochloride Oral Solution* will be administered to participants at their prescribed dose or less for its indicated use (maintenance therapy for opioid use disorder). Using our standard procedure, we will procure the participant's written permission to contact his or her provider to confirm (1) the participant's enrollment in a methadone maintenance program for opioid dependence, (2) the participant's daily dose of methadone and (3) the length of time the participant has been maintained on their current dose. Methadone will be administered in a way that is within the participant's normal dosing regimen with the exception that we will be administering it at our residential research unit and that one dose will be less than what is normally prescribed (Day 1), another dose will be omitted (Day 2) and the final dose may be delayed (Day 3). Methadone is a commercially-available Schedule II medication that is currently indicated for management of pain, detoxification treatment of opioid addiction and maintenance treatment of opioid addiction.

Following oral administration, the bioavailability of methadone ranges between 36 to 100% and peak plasma concentrations are achieved between 1 and 7.5 hours. Published reports indicate that after multiple dose administration the apparent plasma clearance of methadone ranged between 1.4 and 126 L/h, and the terminal half-life (T1/2) was highly variable and ranged between 8 and 59 hours in different studies. Methadone undergoes hepatic N-demethylation by cytochrome P450enzymes, principally CYP3A4, CYP2B6, CYP2C19 and to a lesser extent by CYP2C9 and CYP2D6. Since methadone is lipophilic, it has been known to persist in the liver and other tissues. The slow release from the liver and other tissues may prolong the duration of methadone action despite low plasma concentrations.

b. Justification and safety information if FDA approved drugs will be administered for non-FDA approved indications or if doses or routes of administration or participant populations are changed.

*Cannabidiol:* Cannabidiol is a constituent of the cannabis plant that is being actively investigated for efficacy in a wide range of potential indications (including anxiety and alcohol/substance use disorders, as evidenced by clinicaltrials.gov entries) because of its unique pharmacological mechanisms of action. Specifically, it acts as an inverse agonist on the cannabinoid CB1 and CB2, as a 5-HT1a agonist, as a positive modulator of the transient receptor vallinoid-1 (TRPV1) receptor, and as an allosteric modulator of the mu and delta opioid receptors. The only empirical human studies that have examined the effects of cannabidiol in the context of opioid use reported that cannabidiol can reduce opioid craving and associated anxiety in persons with opioid use disorder. There is preclinical support that the endocannabinoid system is influential in the expression of opioid withdrawal. Cannabinoid type 1 (CB1) receptors are co-localized with mu-opioid receptors and cannabinoid agonists and endocannabinoid catabolic enzyme inhibitors have all shown evidence for opioid withdrawal suppression. Furthermore, over the last 40 years, preclinical evidence has accumulated indicating that CBD can mitigate symptoms of opioid withdrawal and decrease opioid seeking behavior in rodent models. Together these data suggest that CBD warrants further examination as a legitimate treatment for opioid withdrawal symptoms. Safety studies have demonstrated

that CBD is well-tolerated in combination with the highly potent opioid fentanyl among individuals with a history of opioid use disorder. Finally, unlike some other cannabinoids, cannabidiol is believed to be relatively void of euphoric and psychoactive effects, as evidenced by an abuse liability examination that reported therapeutic (750mg) and supratherapeutic doses (1500mg and 4500mg) demonstrated little to no signal for abuse potential relative to alprazolam and dronabinol comparators.

Epidiolex will be administered via the oral route, which is the FDA-approved route of administration.

c. Justification and safety information if non-FDA approved drugs without an IND will be administered.

#### N/A

#### 7. Study Statistics

a. Primary outcome variable.

Feasibility:

- Number of participants who complete the study as intended
- Peak change in withdrawal scores (Subjective Opiate Withdrawal Scale; SOWS) during abstinence-induced withdrawal- this will provides evidence that withdrawal will be sufficiently quantifiable to use this model to examine Epidiolex suppression of withdrawal in a large-scale R01-type trial.

Safety:

- Frequency of Adverse Events (excluding symptoms of opioid withdrawal) reported under each condition (0, 800mg CBD)
- Number of participants whose AST/ALT levels >3xULN at the end of the session according to a blood test at the end of the active drug condition

Initial Efficacy:

- Efficacy will be assessed by comparing the following outcomes between the active (CBD) and placebo-dosing sessions:
  - Withdrawal symptom suppression, measured through daily self-report ratings of withdrawal on the SOWS, evaluated as Total score and individual scores. Scores will be evaluated using area-under-the-curve for each day as well as peak daily rating.
  - Number of 30-minute intervals for which the participant selected money over methadone during the methadone evaluation task

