Over the last 40 years, preclinical evidence has accumulated indicating that CBD can mitigate symptoms of opioid withdrawal and decrease opioid seeking behavior in rodent models. In clinical research, retrospective analyses indicate that the use of cannabis products may be helpful for increasing opioid treatment retention. Two human lab studies (N=6 and n=42) on this topic demonstrated that a single dose of oral CBD decreased cue-induced craving and anxiety (two common withdrawal symptoms) among recently abstinent heroin-dependent individuals relative to placebo. In an effort to further characterize the clinical utility of CBD, we recently conducted a crowdsourcing survey study which determined that individuals with OUD with CBD use indicated that CBD helped mitigate the following opioid withdrawal symptoms: anxiety (76%), sleep problems (45%), restlessness (36%), and/or bone/muscle aches (36%).

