This will be a within subject comparison. Each participant will attend two 3-day inpatient sessions during which they will receive active drug during one session and placebo on the other. The placebo will be a flavor-matched cherry liquid syrup. 2 syringes of 10mL of Study Drug + Flavored syrup (4mL Epidiolex, 6mL flavored syrup per syringe) and 2 syringes of 10mL Placebo (flavored syrup) will be administered via the oral route under double-blind conditions. The sequence of the sessions (Placebo, Active or Active, Placebo) will be randomized and counter-balanced for all participants. Note that we do not anticipate safety issues with Epidiolex because of its extremely high safety profile. Participants will take the study drug once every 12 hours and will receive a total of 4 doses. This dosing regimen has been selected based upon evidence that four doses are required for Epidiolex to reach steady-state levels and that this dosing regimen is well-tolerated (23). Cannabidiol (Epidiolex) will be flavor-masked with cherry-syrup by our research pharmacy to ensure double-blind administration. Epidiolex dose and cherry syrup will be delivered in 2 x 10 mL oral syringes.

Eligible participants will attend two residential sessions that will last 3-days/2-nights. Study procedures will take place at the Behavioral Pharmacology Research Unit's Residential Research Unit (RRU) and the Clinical Research Unit (CRU); both located on the Johns Hopkins Bayview Medical Campus. Previous studies suggest this design will provide a sufficient observation period to produce abstinence-induced withdrawal (24). Patients will be instructed to arrive at the BPRU the morning of Day 1. Research staff will contact the participant's methadone prescribing clinic to confirm the participant did not receive their dose JHMIRB eFormA 01

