#### 8. Risks

a. Medical risks, listing all procedures, their major and minor risks and expected frequency.

Risks Associated with Cannabidiol: Cannabidiol has few contraindications. It should not be administered to persons with known sensitivity to cannabidiol. Epidiolex is extensively metabolized by the liver, therefore persons with moderate-severe hepatic impairment (defined in the FDA product label as ALT or AST levels >3x ULN and/or Bilirubin levels >2x ULN) who might have different plasma concentrations of Epidiolex as a result of liver impairment will also be excluded. Epidiolex has been reported to produce somnolence or sedation in up to 32% of patients (compared to 11% of patients receiving placebo) and this may be further exacerbated in persons who are taking other CNS depressants. The FDA also recommends that persons receiving any antiepileptic drug, of which Epidiolex is one, be screened for suicidal behaviors prior to beginning drug administration. Additional side effects reported in clinical trial examinations of Epidiolex for seizure indications in adult and child populations include decreased appetite, diarrhea, weight decrease, gastroenteritis, lethargy, fatigue/malaise, insomnia, irritability/agitation, drooling, gait disturbance, rash, hypoxia, and infections. A determination of the safety of CBD during pregnancy has not yet been made.

Risks Associated with Methadone: The risks associated with methadone are well known and it is notable that we will not be administering any dose of methadone that is higher than the dose the participant already receives as part of his or her routine methadone maintenance treatment. The potential acute side effects of methadone relevant to our protocol include constipation, nausea, sleepiness, vomiting, tiredness, headache, dizziness, and abdominal pain. Like other opioids, methadone is contraindicated in patients with respiratory depression or acute bronchial asthma or hypercarbia.

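### The primary adverse event count excludes opioid withdrawal symptoms without a list or attribution rule, so a CBD–placebo difference in an overlapping event such as insomnia could be distorted in that count

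*Combined protocol and SAP*

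**What the plan says.** Section 7a (Study Statistics, primary outcome variable) gives two safety outcomes. The first is "Frequency of Adverse Events (excluding symptoms of opioid withdrawal) reported under each condition (0, 800mg CBD"; the second is the number of participants whose AST/ALT exceeds three times the upper limit of normal at the end of the active session. The first carries an exclusion, but neither section 7a nor any other section lists the excluded symptoms, ties the exclusion to the items of a scale, or says who attributes an event and how. Sections 8a to 8c promise monitoring and weekly review only in general terms.

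Section 8a names side effects of Epidiolex that "include decreased appetite, diarrhea, weight decrease, gastroenteritis, lethargy, fatigue/malaise, insomnia, irritability/agitation, drooling, gait disturbance, rash, hypoxia, and infections", and says they were "reported in clinical trial examinations of Epidiolex for seizure indications in adult and child populations". Section 3 (Background) cites a survey in which respondents said CBD helped with these "opioid withdrawal symptoms: anxiety (76%), sleep problems (45%), restlessness (36%), and/or bone/muscle aches (36" per cent).

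Both sessions induce withdrawal by design (section 4a), and study drug "will be administered via the oral route under double-blind conditions". Section 4c states the hypothesis that CBD lessens some withdrawal symptoms. Section 8a expects that the likeliest interaction effect is later onset of methadone withdrawal, to be seen against the placebo session. Section 7c says that results will mainly be described rather than tested.

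**The concern.** An outcome that removes events by presumed cause needs a rule for assigning cause, above all where the study deliberately produces the competing cause in every session. Insomnia stands on the protocol's own list of drug side effects and, as sleep problems, among the withdrawal symptoms it names. Irritability/agitation overlaps with anxiety or restlessness, though only by inference. Each such event can be counted or left out at someone's discretion.

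Safety within the withdrawal paradigm is the first objective in section 2. The adverse event count is the only safety outcome in section 7 that covers symptoms: AST/ALT does not, and the study-level stopping rules in section 7d use only death and AST/ALT. Because the results are descriptive and are meant as preliminary data for a grant application, a distorted count would be carried forward as it stands.

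**Working it through.** **Is there a stated figure to reproduce?** No. The documents give no sample size, expected adverse event count, insomnia rate or attribution share. What follows shows direction and mechanism only.

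**Step 1: the overlap, from the documents.** Section 8a lists 13 side-effect terms in the sentence quoted above. One, insomnia, matches a withdrawal symptom named in section 3. A second, irritability/agitation, matches by inference. Section 3 reports a survey and does not define withdrawal, so it cannot be told how many of the other 11 terms would be excluded.

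**Step 2: the formula.** Let
- b = background percentage of participants with the event (placebo session);
- d = true CBD excess, in percentage points;
- fP, fC = share of such events classed as withdrawal, and so excluded, in the placebo and CBD sessions.

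Counted on placebo: b(1 − fP). Counted on CBD: (b + d)(1 − fC).

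Displayed difference = (b + d)(1 − fC) − b(1 − fP).

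If fP = fC = f, this reduces to d(1 − f), whatever b is.

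**Step 3: numbers.** Assumed, not from the documents: b = 30, d = 20, and every share.

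| fP | fC | Placebo counted | CBD counted | Displayed difference |
|---|---|---|---|---|
| 0 | 0 | 30 | 50 | 20 (no loss) |
| 0.25 | 0.25 | 22.5 | 37.5 | 15 |
| 0.5 | 0.5 | 15 | 25 | 10 |
| 0.75 | 0.75 | 7.5 | 12.5 | 5 |
| 1 | 1 | 0 | 0 | 0 (lost) |
| 0.7 | 0.5 | 9 | 25 | 16 |
| 0.9 | 0.4 | 3 | 30 | 27 (inflated) |
| 0.5 | 0.7 | 15 | 15 | 0 |
| 0.5 | 0.75 | 15 | 12.5 | −2.5 (reversed) |

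With d = 10 the equal-share results halve: 10, 7.5, 5, 2.5 and 0.

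**Step 4: can the shares differ under blinding?** Yes. Blinding hides the label, but whoever judges the event still sees the clinical picture. If CBD reduces or delays withdrawal, as sections 4c and 8a anticipate, sleeplessness in the CBD session may come with fewer other withdrawal signs and be called withdrawal less often (fC below fP). That pushes the displayed difference upward. Reversal needs fC well above fP. The documents give no particular reason to expect that, but without a rule nothing excludes it.

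**Step 5: what is not affected.** Section 8a reports somnolence or sedation in up to 32% of patients against 11% on placebo, a gap of up to 32 − 11 = 21 points. It is not among the withdrawal symptoms named in section 3, so on the same overlap test it would stay in the count. Rash and AST/ALT should also be untouched, as should the vital signs: "Vital signs will also be measured every time withdrawal assessments occur".

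**The case against.** The strongest reply has four parts.

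*The exclusion has a purpose.* If CBD relieves withdrawal, an all-cause total could fall on CBD and mask other events. This stands, and it is why the exclusion should be kept as one of two displays rather than dropped.

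*The overlap is thin.* One term matches by name, and the source is a survey. The exclusion might be meant to follow the SOWS, the only withdrawal scale in section 7a; its items are not given, so the documents do not show that insomnia would be excluded. This stands as a limit on certainty. It also restates the problem, since the reader cannot tell what is excluded.

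*Other measures would show it.* Participants complete "withdrawal ratings on a regular basis (e.g., every 4 hours) before and after study drug administration, except for when the participant is sleeping", SOWS individual scores are compared between sessions, and participants "complete measures of drug craving and anxiety periodically throughout Day 1". This gives partial coverage. The SOWS comparison sits under efficacy with its items unstated, and the anxiety measure is not a section 7 outcome.

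*Blinded, within-participant dosing makes misclassification equal, so the worst case is dilution.* A reader might infer this, and equally that the sign cannot reverse. Neither is supported: both hold only if the shares are equal, and the protocol's own expectations about withdrawal give a reason why they may not be.

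A reader might also infer that a known insomnia effect is being hidden. The documents do not support that either. The side-effect list comes from seizure trials in adults and children, and each session here has four doses, so an insomnia excess is possible but not shown to be expected.

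**Conclusion.** The point holds as a defect in the definition of a primary safety outcome. The exclusion has no list and no attribution rule, and at least one listed side effect falls on both sides of the line. A CBD–placebo difference in such an event could be diluted, lost, inflated or reversed in this count, depending on shares that the documents do not give.

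The real size cannot be computed. The illustrative range of −2.5 to 27 points around a true 20 rests wholly on the assumed background, excess and shares, and no distortion at all (both shares zero) is also possible. The rest of the safety assessment, including the one symptom with stated rates, should be unaffected. For a descriptive pilot the severity is minor to moderate; it is worth correcting because the placebo session already supplies the background rate that makes judging cause unnecessary.

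**What to change.** Amend section 7a along these lines:

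> All adverse events will be recorded and tabulated by term regardless of presumed cause, as the number of participants with at least one event and the number of events in each session (CBD versus placebo). Totals will be shown with and without the withdrawal symptoms listed here, a list fixed before unblinding.

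Write the list into section 7a. The SOWS items are a natural starting point, and the list should say expressly whether insomnia and irritability/agitation are on it. A fixed list of terms makes the excluded share either 0 or 1 for each term and the same in both sessions, so unequal attribution no longer arises. The by-term rows and the unrestricted total keep what the list removes. These rows show a net difference between sessions; they do not establish the cause of any single event.

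Confirm as well that withdrawal-type events are recorded as adverse events. If they are now captured only on the SOWS, the recording instruction must change too, because no table can recover what was never recorded.

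The cost is some wording, a longer table with more background events in both sessions, and possibly that instruction. The all-cause total may fall if CBD relieves withdrawal, which is why both totals are shown.
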